4.2.7. DAS28-CRP

Results of DAS28-CRP are calculated directly in the eCRF and validated according to the Data Validation Plan, so no additional derived variables are necessary.

For clarity, formula used for DAS28-CRP in the eCRF is shown here:

$$DAS28-CRP = 0.56 * \sqrt{t28} + 0.28 * \sqrt{s28} + 0.36 * \log(CRP + 1) + 0.014 * pgf + 0.96$$

Where:

t28 – sum of tender joints

s28 – sum of swollen joints

CRP – concentration of CRP protein expressed in mg/l.

Classification of disease activity is performed in the eCRF based on the following DAS28-CRP breakpoints:

<3.2 – Low disease activity

<3.2 – 5.1> – Moderate disease activity

>5.1 – High disease activity

Moreover, DAS28-CRP score lower than 2.6 will be classified as remission.

4.2.8. Response states classified by change in DAS28-CRP

Based on DAS28-CRP score subjects can be classified into following response states:

- Good responder: improvement of more than 1.2 on DAS28-CRP score and a present score of at maximum 3.2.
- Moderate responder: improvement of more than 0.6 but no more than 1.2 and a present score of at maximum 5.1 OR improvement of more than 1.2 and a present score more than 3.2.
- Non-responder: improvement of no more than 0.6 OR improvement of more than 0.6 but no more than 1.2 and a present score of more than 5.1.

4.2.9. DAS28-ESR

For additional analysis DAS28-ESR is calculated according to the formula (Leong et al, 2020):

$$DAS28-ESR = 0.56 * \sqrt{t28} + 0.28 * \sqrt{s28} + 0.7 * \log(ESR) + 0.014 * pgf$$

Where:

t28 – sum of tender joints

s28 – sum of swollen joints

ESR – erythrocyte sedimentation rate [mm].

4.2.10. Health Assessment Questionnaire – Disability Index (HAQ-DI)

Results of HAQ-DI are calculated directly in the eCRF and validated according to the Data Validation Plan, so no additional derived variables are necessary.

4.2.11. 36-Item Short Form Survey Instrument (SF-36 RAND)

Results of SF-36 RAND are calculated directly in the eCRF and validated according to the Data Validation Plan, so no additional derived variables are necessary.

4.2.12. Functional Assessment of Chronic Illness Therapy – Fatigue (FACIT-F)

Results of FACIT-F are calculated directly in the eCRF and validated according to the Data Validation Plan, so no additional derived variables are necessary.

4.2.13. American College of Rheumatology assessment (ACR)

The American College of Rheumatology's (ACR20) definition for calculating improvement in RA is calculated as:

- A 20% improvement in tender joint count (68),
- A 20% improvement in swollen joint count (66),
- A 20% improvement in at least 3 of the following 5 remaining ACR-core set measures:
 - patient global assessments (PtGA),
 - physician global assessments (PhGA),
 - pain (PAAP),
 - disability (HAQ-DI),
 - an acute-phase reactant (CRP).

Similarly, ACR50, ACR70 and ACR90 are calculated with the respective percent improvement.

Improvement in each of those measures will be calculated as:

$$\text{Measure improvement} = (\text{Measure at Visit} - \text{Measure at Day 1}) / \text{Measure at Day 1} * (-100\%)$$

As in all of those ACR-core set measures improvement is defined as lower value of the measure, in the equation above there is multiplication by minus 100%, so the result would be informing about improvement percentage.

4.2.14. Targeted medical adverse events

Any of the AEs that occurred on (or after) the day of the first IMP administration that meets one of the following criteria:

SOC belongs to group “Infections and infestations”

OR HLGT belongs to a group “Embolism and thrombosis”

OR PT is “Gastrointestinal perforation”

OR (SOC belongs to a group “Cardiac disorders” AND AE is classified as Serious).

OR SOC belongs to group “Neoplasms benign, malignant and unspecified (incl cysts and polyps)”

OR PT is “Hypotension”

OR PT is “Blood pressure abnormal”

where:

PT – MedDRA Preferred Term

HLGT – MedDRA High Level Group Term

SOC – MedDRA System Organ Class.

Preliminary list prepared by the data management team will be reviewed by medical monitor and confirmed during blinded data review meeting.

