### **Recording of Adverse Events**

Adverse events should be collected and recorded for each subject from the date the ICF is signed until the end of their participation in the study, i.e. the subject has discontinued or completed the study.

Adverse events may be reported spontaneously by the subject, or discovered by the study staff during physical examinations or by asking an open, non-leading question such as 'How have you been feeling since you were last asked?' All AEs and any required remedial action will be recorded. The nature of AE, date (and time, if known) of AE onset, date (and time, if known) of AE outcome to date, severity and action taken of the AE will be documented together with the Investigator's assessment of the seriousness of the AE and causal relationship to study drug and/or study procedure.

All AEs should be recorded individually in the subject's own words (verbatim) unless, in the opinion of the Investigator, the AEs constitute components of a recognized condition, disease or syndrome. In the latter case, the condition, disease or syndrome should be named rather than each individual symptom. The AEs will subsequently be coded using the Medical Dictionary for Regulatory Activities (MedDRA).

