2.1.2. Secondary endpoints

Clinical Efficacy:

- Proportion of subjects with DAS28-CRP remission at Weeks 4; 8; 12 and 16.
- American College of Rheumatology (ACR)20, ACR 50, ACR 70, and ACR 90 responder rates (Weeks 4, 8 and 12).
- Change from Baseline in the Tender/Painful and Swollen Joint Count (Weeks 4, 8 and 12).
- Change from Baseline in the Physician's Global Assessment (PhGA) of Arthritis (Weeks 4, 8 and 12).

Patient Reported Outcome:

- Change from baseline in the Patient's Assessment of Arthritis Pain (PAAP) VAS and Patient Global Assessment of Arthritis (PtGA, VAS) at Week 4, 8, and 12.
- Change from baseline in the Health Assessment Questionnaire – Disability Index (HAQ-DI) at Week 4, 8, and 12.
- Change from baseline in the SF-36 RAND 8 Domain scores and Physical Component Score (PCS) and Mental component score (MCS) at Week 12.
- Change from baseline in the Functional Assessment of Chronic Illness Therapy Fatigue (FACIT-F) total score at Week 12.

Safety:

Safety and tolerability of CPL409116: vital signs (blood pressure (BP), pulse and temperature), laboratory tests, Adverse Events (AEs) and Serious Adverse Events (SAEs), 12-lead electrocardiogram (ECG):

- Incidence and severity of adverse events, serious adverse events, and withdrawals due to adverse events (Baseline through Week 16).
- Incidence of abnormality in clinical chemistry parameters (Baseline through Week 16).
- Incidence of abnormality in haematological parameters (Baseline through Week 16).
- Change from baseline in blood pressure measurement (Baseline through Week 16).
- Change from baseline in pulse rate measurement (Baseline through Week 16).
- Change from baseline in temperature measurement (Baseline through Week 16).
- Incidences of targeted medical adverse events (Baseline through Week 16).

Pharmacokinetics:

- CPL409116 and metabolite M3 pharmacokinetic variables: $AUC_{(0-6h)}$, C_{max} , T_{max} , $T_{1/2}$ (if possible) and K_{el} (if possible) determined on Day 1, 8, 57 and 85.
- CPL409116 pharmacokinetic variables: C_{0h} , $C_{2.5h}$ determined on Day 29.

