4.12.1. Adverse events analysis

Any undesirable signs, symptoms or medical conditions occurring or worsening of pre-existing conditions between signing informed consent and the first administration study medication are considered as pre-treatment AEs. Undesirable signs, symptoms or medical conditions or worsening of pre-existing conditions occurring after the first administration of study medication are considered as treatment emergent adverse events (TEAEs).

A TEAE will be analyzed as related to study medication (i.e. as adverse drug reaction, ADR) if the relationship to study treatment was documented as 'unlikely', 'possible', 'probable', or 'definite' or if the relationship to study treatment is missing.

An overview table presenting the incidence of the following AE categories will be presented. Percentage of patients in each category will be compared between treatments as a difference in proportions between treatments including a 95% CI based on the Agresti – Caffo method (2000):

- All AEs
- Pre-treatment AEs
- Serious AEs (SAEs) (including pre-treatment SAEs)
- Treatment emergent AEs (TEAEs)
- Treatment emergent SAEs (TESAEs)
- Severe TEAEs
- Related TEAEs
- Related severe TEAEs
- TEAEs leading to reduction of dose
- TEAEs leading to interruption of dose
- TEAEs leading to permanent discontinuation (i.e. withdrawal) of study medication
- Related TEAEs leading to permanent discontinuation of study medication
- AEs leading to death (i.e. outcome of AE is fatal)
- TEAEs leading to death
- Related TEAEs leading to death
- Targeted medical adverse events

Targeted medical adverse events are defined in section 4.2.14.

All treatment emergent AEs (TEAEs) and all serious TEAEs will be tabulated by MedDRA System Organ Class (SOC) and preferred term (PT) presenting the number and percentage of patients reporting the AE and the number of AEs reported. Additional tables will distinguish the events by whether the AE was related to study medication and by maximum severity.

All AEs documented in the eCRF will be listed by patient. Data listings will include patient ID, treatment group, verbatim term, preferred term, system organ class, start and stop date and relative day of the AE, severity, medications (yes/no), seriousness, action taken with study medication, relationship to study medication, and outcome will be provided. TEAEs will be

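### SAP 4.2.14 picks up gastrointestinal perforation by one exact preferred term and blood pressure by two, so the same kind of event coded to another term would not be flagged for the targeted-AE row

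*SAP*

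**What the plan says.** SAP 2.1.2 lists "Incidences of targeted medical adverse events (Baseline through Week 16" among the secondary safety endpoints. The protocol synopsis names the same endpoint without defining it, so SAP 4.2.14 is the only definition.

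That section starts from every AE on or after the day of first dosing and keeps those that meet any of seven criteria. Four work at class or group level:
- the infections SOC;
- the neoplasms SOC;
- the cardiac SOC, serious events only;
- the embolism and thrombosis HLGT.

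Three are exact preferred terms: "OR PT is “Gastrointestinal perforation", "OR PT is “Hypotension" and "OR PT is “Blood pressure abnormal".

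The section then adds a review step: "Preliminary list prepared by the data management team will be reviewed by medical monitor and confirmed during blinded data review meeting".

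The result is one row of the AE overview table in SAP 4.12.1, where "Percentage of patients in each category will be compared between treatments as a difference in proportions between treatments including a 95% CI", by the Agresti-Caffo method.

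On how terms arise, Protocol 8.1 (Recording of Adverse Events) says: "All AEs should be recorded individually in the subject's own words (verbatim". The exception is events that the investigator judges to be components of a recognised condition, which is then named instead. MedDRA coding follows.

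**The concern.** A class- or group-level criterion does not depend on the wording of the report, provided the event falls in that class. An exact-PT criterion does: two reports of the same clinical event can be coded to different PTs, and only one of them passes the filter. The plan uses the fragile form for perforation and blood pressure and the robust form for everything else, and gives no reason for the difference.

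At stake is the count of patients in one pooled row. The row is a stated endpoint and is compared between arms with a confidence interval. In arms of 25, one patient is visible in the percentage.

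**Working it through.** **Text comparison**

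| Concept | Rule in SAP 4.2.14 | Depends on exact PT? |
|---|---|---|
| Infections | SOC | no |
| Neoplasms | SOC | no |
| Cardiac, serious | SOC plus seriousness | no |
| Thromboembolism | HLGT | no |
| Gastrointestinal perforation | one PT | yes |
| Blood pressure | two PTs | yes |

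The SAP itself lists two PTs for blood pressure, which shows that one concept can span more than one PT. The documents contain no MedDRA term list. That further PTs exist for perforation or blood pressure is therefore an assumption.

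If the preliminary list is the output of this filter, an event that the filter excluded is not on it. Reviewing that list does not bring the event back.

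**Size**

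The plan gives no figure for this row, so there is none to reproduce. The calculation below only shows scale.

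Inputs: 25 patients per arm (SAP 2.2); Agresti-Caffo 95% interval (SAP 4.12.1); event counts assumed.

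Formulas:
- adjusted proportion p = (x + 1)/(n + 2), with x the number of patients with a targeted event and n the arm size;
- difference d = p(active) − p(placebo);
- SE = √[p(active)(1 − p(active))/(n + 2) + p(placebo)(1 − p(placebo))/(n + 2)];
- interval d ± 1.96 SE.

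Effect of one missed patient:
- arm percentage: 1/25 = 4.0 points;
- Agresti-Caffo difference: 1/27 = 3.7 points.

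Worked case, assuming true counts of 5/25 active and 4/25 placebo:
- p(active) = 6/27 = 0.2222 and p(placebo) = 5/27 = 0.1852, so d = 0.0370;
- SE = √[(0.2222 × 0.7778 + 0.1852 × 0.8148)/27] = 0.1095;
- half-width 1.96 × 0.1095 = 0.215, or 21.5 points.

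| Counted active / placebo | Difference, points | 95% CI |
|---|---|---|
| 5 / 4 (none missed) | 3.7 | −17.8 to 25.2 |
| 4 / 4 (one active patient missed) | 0.0 | −20.7 to 20.7 |
| 5 / 3 (one placebo patient missed) | 7.4 | −13.2 to 28.0 |

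A miss lowers the count in its own arm, so the difference can move either way depending on the arm. The shift is 3.7/21.5 = 17% of the half-width, and all three intervals include zero. The shift arises only if the missed patient has no other targeted event.

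**The case against.** The strongest objection is that a correction step already exists. The list is called preliminary, it is reviewed by the medical monitor, and it is confirmed at a blinded meeting. Those words imply that something can change, and Protocol 12.1 lets the Medical Monitor review safety information throughout the study. A reader might infer that the review cannot correct the list. The text does not support that; it leaves the scope unstated. SAP 4.2.16 does say that the medical monitor may update its drug list, and SAP 3.3 describes the data review meeting only for protocol deviations, but silence in 4.2.14 is missing detail, not a prohibition. What stands against the objection is narrower: a review confined to flagged events does not recover unflagged ones.

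A second objection is that the miss rests on MedDRA terms outside the documents. That is fair, and it is why the point is stated with an assumption. The two blood-pressure PTs support it for blood pressure; nothing in the documents bears directly on perforation. The recorded term may also be less variable than verbatim recording suggests, because a recognised condition is to be named as such.

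A third objection is that little is lost. SAP 4.12.1 tabulates all treatment-emergent AEs by SOC and PT, lists all AEs, and lists serious AEs, deaths and discontinuations separately. A perforation that led to hospital admission would be a serious AE. Blood pressure also has its own endpoint, "Change from baseline in blood pressure measurement (Baseline through Week 16". All of this stands and limits the severity.

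A reader might also infer that Blood pressure abnormal over-counts, because it states no direction and would admit high readings. The documents do not support this. Neither document says that low pressure is the only target, the vital-sign shift tables in SAP 4.12.3 cover both directions, and the term may be a deliberate catch-all.

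**Conclusion.** The point holds as a minor weakness of method. Read literally, the perforation and blood-pressure criteria can leave out an event that belongs in the row, while the other four criteria do not turn on a single PT. One missed patient moves an arm's rate by 4.0 points and the adjusted difference by 3.7 points.

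This rests on four conditions:
- other PTs for these concepts exist in the MedDRA version used;
- an event is coded to one of them;
- the patient has no other targeted event;
- the review does not look beyond the flagged list.

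How often all four hold together cannot be derived from the documents.

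It would be too strong to infer that safety events vanish from the report. They remain in the SOC/PT tables and the listings, so the gap is confined to one pooled row. The primary endpoint, the significance level and the sample size are not affected.

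**What to change.** Before unblinding, amend SAP 4.2.14 as follows.

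1. Replace the single perforation PT with a pre-specified list of perforation PTs, or with the corresponding standardised MedDRA query if the version in use has one.
2. Do the same for blood pressure, keeping Blood pressure abnormal on the list as the sponsor chose.
3. State that the filter runs over all treatment-emergent AEs, and that its output is the list given to the medical monitor.

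The cost is a short term list and a few lines of SAP text; no new data are needed. The downside is a few more candidate events for the medical monitor to review.

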4.2.15. Laboratory values

Laboratory values below the lower limit of quantification (LLOQ) will be set to $\frac{1}{2} \times \text{LLOQ}$ and those greater than upper limit of quantification will be set to this limit.

4.2.16. Prior, rescue and concomitant medication

Prior medications are those with an end date of administration prior to the date of the first IMP administration.

Concomitant medications are those that started or continued during the study treatment period.

List of drugs classified as rescue medications will be prepared based on assessment performed by Medical Monitor and presented during BDRM.

Classification of drugs into Disease-Modifying and Anti-Rheumatic Drugs (DMARDs), glucocorticosteroids, Non-Steroidal Anti-Inflammatory Drugs (NSAIDs) will be based on ATC codes presented below. This list may be updated before the final database lock by a medical monitor.

Table 4. Prior medication classification for purpose of baseline characteristics

ATC code for the group	ATC code for the group	ATC code for cmpd	Name
c/tsDMARDs	A07EC Aminosalicylic acid and similar agents	A07EC01	sulfasalazine
	L01BA Folic acid analogues	L01BA01 (iv)	methotrexate
	L04AA - Selective immunosuppressants;	L04AA01	cyclosporine
		L04AA13	leflunomide
	L04AX - Other immunosuppressants	L04AX01	azathioprine
		L04AX03 (oral)	methotrexate
		M01CB01	sodium aurothiomalate
	M01CB Gold preparations;	M01CB03	auranofin
		M01CB04	aurothioglucose
		P01BA02	hydroxychloroquine
bDMARDs	L04AA - Selective immunosuppressants	L04AA11	etanercept
		L04AA12	infliximab
		L04AA14	anakinra
		L04AA17	adalimumab

		L04AA24	abatacept
	L04AB - Tumor necrosis factor alpha (TNF- α) inhibitors	L04AB05	certolizumab
		L04AB06	golimumab
	L04AC - Interleukin inhibitors	L04AC07	tocilizumab
	L01XC - Monoclonal antibodies	L01XC02	rituximab
ATC code for the group	ATC code for the group	ATC code for cmpd	Name
Glucocorticosteroids	H02AB	H02AB04	methylprednisolone
		H02AB06	prednisolone
		H02AB07	prednisone
		H02AB13	deflazakort
ATC code for the group	ATC code for the group	ATC code for cmpd	Name
Non-Steroidal Anti-Inflammatory Drugs (NSAIDs)	M01AA - Butylpyrazolidines	M01AA01	phenylbutazone
	M01AB - Acetic acid derivatives and related substances	M01AB01	indometacin
		M01AB02	sulindac
		M01AB03	tolmetin
		M01AB05	diclofenac
		M01AB08	etodolac
		M01AB15	ketorolac
		M02AA25	Aceclofenac
	M01AC - Oxicams	M01AB55	diclofenac in combination
		M01AC01	piroxicam
		M01AC02	tenoxicam
		M01AC05	lornoxicam
	M01AE - Propionic acid derivatives	M01AC06	meloxicam
		M01AE01	ibuprofen
		M01AE02	naproxen
		M01AE03	ketoprofen
		M01AE04	fenoprofen
		M01AE09	flurbiprofen
		M01AE11	tiaprofenic acid
	M01AG - Fenamates	M01AE12	oxaprozin
		M01AG01	mefenamic acid
		M01AH01	celecoxib
		M01AH05	etoricoxib
	M01AH - Coxibs	M01AH02	rofecoxib
		M01AH03	valdecoxib

	M01AX - Other antiinflammatory and antirheumatic agents, non-steroids	M01AX01	nabumetone
	M02AA Antiinflammatory preparations, non-steroids for topical use	M02AA26	nimesulide
	M02AC - Preparations with salicylic acid derivatives	M02AC	preparation with salicylic acid derivatives

4.2.17. Pharmacokinetic and pharmacodynamic parameters

The pharmacokinetic parameters will be computed using non-compartmental modelling approach using actual sampling times. The pharmacokinetic parameters will be derived individually for each subject and day of study, if applicable.

PK parameters listed below will be estimated for both CPL409116 and its metabolite M3, if data permits.

PK parameters listed in the Clinical Trial Protocol:

- $AUC_{(0-6h)}$: The area under the curve of plasma concentration vs time, from time point zero up to 6 hours after drug administration, unit: [ng*h/mL]. $AUC_{(0-6h)}$ will be calculated according to the linear trapezoidal rule. To be calculated for Days 1, 8, 57 and 85.
- C_{max} : Maximum plasma concentration, unit: [ng/mL]. C_{max} defines the maximum concentration of the drug substance (or metabolite) in plasma during administration period. C_{max} will be obtained directly from the measured concentrations. If multiple peaks occur, the highest postdose concentration will be reported as C_{max} . To be calculated for Days 1, 8, 57 and 85.
- T_{max} : Time to reach maximum plasma concentration, unit: [h]. T_{max} will be obtained directly from the actual sampling times. In the case that multiple peaks are of equal magnitude, the earliest T_{max} will be reported. To be calculated for Days 1, 8, 57 and 85.
- K_{el} : Terminal elimination rate constant, unit: [1/h]. K_{el} will be estimated via linear regression of time versus log of concentration. This parameter will be calculated by linear least squares regression analysis using at least last three non-zero plasma concentration values. C_{max} values will not be included in K_{el} calculation. K_{el} will only be calculated if the adjusted coefficient of determination of exponential fit (R^2 adjusted) is not less than 0.7 ($R^2 \geq 0.7$). To be calculated for Days 1, 8, 57 and 85.
- $T_{1/2}$: Plasma elimination half-life, unit: [h]. $T_{1/2}$ will be calculated as $\ln(2)/K_{el}$. To be calculated for Days 1, 8, 57 and 85.

Exploratory PK parameters:

- $AUC_{(0-\infty)}$: The area under the curve of plasma concentration vs time, from time point zero extrapolated to infinity, unit: [ng*h/mL]. $AUC_{(0-\infty)} = AUC_{(0-t)} + C_t/K_{el}$, $AUC_{(0-t)}$ is the area under the curve of plasma concentration vs time from time point zero to the last measurable analyte concentration in plasma, C_t is the last measurable analyte concentration in plasma and K_{el} is the terminal elimination rate constant. To be calculated for Days 1, 8, 57 and 85.
- $AUC_{(0-t)}$: The area under the curve of plasma concentration vs time, from time point zero to the last measurable analyte concentration in plasma, unit: [ng*h/mL]. $AUC_{(0-t)}$ will be calculated according to the linear trapezoidal rule. To be calculated for Days 1, 8, 57 and 85.
- AUC_{tau} : The area under the curve of plasma concentration vs time, from dosing time to dosing time plus tau (12 h), unit: [ng*h/mL]. AUC_{tau} will be calculated according to the linear trapezoidal rule. To be calculated for Day 85. If dosing time plus tau is not an

exact observation time due to small sampling time deviations, the AUC_{tau} is computed based on an estimated concentration at dosing time plus tau (concentration at dosing time plus tau is estimated using logarithmic interpolation if both observed analyte concentrations last before and first after the time point dosing time plus tau are measurable ($>LLOQ$) and using the linear interpolation otherwise).

- t_{lag} : Time to measurable (non-zero) plasma concentration, unit: [h]. t_{lag} will be obtained directly from the actual sampling times as the last sampling time prior to the first measurable (non-zero) plasma concentration. To be calculated for Day 1.
- CL/F (where F is product absolute availability in oral administration): apparent systemic clearance, will be calculated as dose administered in dosing interval divided by AUC_{tau} at steady state (Day 85), $CL/F = \text{Dose}/AUC_{\text{tau}}$. To be calculated for Day 85.
- MRT: Mean Residence Time will be calculated for Day 85 as ratio of $AUMC_{0-\infty}$ to the AUC_{tau} , where $AUMC_{0-\infty} = AUMC_{\text{tau}} + \tau(AUC_{0-\infty} - AUC_{\text{tau}})$, where C_t is the last measurable concentration, t_z is time of last measurable concentration. To be calculated for Day 85. MRT will be calculated under assumption that mean input time is 0.
- V_z/F : apparent volume of distribution, calculated as $\text{Dose}/(K_{\text{el}} * (AUC_{\text{tau}}))$ at steady state (Day 85) (with limitations as described above). To be calculated for Day 85.
- C_{trough} : the trough concentration is the concentration reached by the drug immediately before the next dose is administered or at 12 h for the last dose. To be calculated for Days 8, 29, 57, and 85. Note: sampling time of 12 h on Day 85 should also be included.
- $C_{\text{max,ss}}$: Maximum blood concentration obtained directly from the measured concentration, at steady state - equivalent to the C_{max} for the Days 8, 57, and 85. To be calculated for Days 8, 57, and 85.
- $C_{\text{min,ss}}$: Minimum blood concentration obtained directly from the measured concentration, at steady state. To be calculated for Days 8, 29, 57, and 85.
- C_{av} : average concentration in the dosing interval, calculated as $AUC_{\text{tau}}/12$ h. To be calculated for Day 85.
- Swing: calculated as $(C_{\text{max,ss}} - C_{\text{min,ss}})/C_{\text{min,ss}} \times 100\%$. To be calculated for Days 8, 57, and 85.
- Fluctuation: calculated as $(C_{\text{max,ss}} - C_{\text{min,ss}})/C_{\text{av}} \times 100\%$. To be calculated for Day 85.
- Accumulation ratio for $AUC_{(0-6h)}$: ratio of $AUC_{(0-6h)}$ on the selected day (d) to the value for Day 1 calculated as $AUC_{(0-6h,d)}/AUC_{(0-6h,1)}$. To be calculated for Days 8, 57, and 85.
- Accumulation ratio for C_{max} : ratio of C_{max} on the selected day (d) to the value for Day 1 calculated as $C_{(\text{max},d)}/C_{(\text{max},1)}$. To be calculated for Days 8, 57, and 85.
- $AUC\%_{\text{Extrap_obs}}$: The percentage of residual area is to be determined by the formula $[(AUC_{(0-\infty)} - AUC_{(0-t)})/AUC_{(0-\infty)}] \times 100\%$. To be calculated for Days 1, 8, 57, and 85.

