4.15. Exploratory analyses of pharmacokinetic data

An exploratory PK analysis, not described in the clinical study protocol, will be performed if data permits for both CPL409116 and M3 individually for each subject (and separately for Days 1, 8, 57, and 85, if applicable):

- $AUC_{(0-t)}$ and $AUC_{(0-\infty)}$ on Day 85
- %extrapolated AUC on Day 85
- metabolite-to-parent ratio of C_{max} and $AUC_{(0-6h)}$ – based on molar concentrations
- accumulation calculated as $AUC_{(0-6h)}$ ratios Day 8/Day 1, Day 57/Day 1 and Day 85/Day 1
- accumulation calculated as for C_{max} ratios Day 8/Day 1, Day 57/Day 1 and Day 85/Day 1
- linearity of dose-normalized C_{max} and $AUC_{(0-6h)}$
- evaluation of changes in T_{max} (median and range, individual differences) between doses and days of study
- evaluation of changes in $T_{1/2}$ (mean \pm SD) on Day 85 between doses
- evaluation of changes in CL/F (mean \pm SD) on Day 85 between doses
- evaluation of changes in Vz/F (mean \pm SD) on Day 85 between doses
- $C_{max,ss}$ on Days 8, 57 and 85
- $C_{min,ss}$ on Days 8, 29, 57 and 85
- evaluation of steady-state basing on C_{trough} on Days 8, 29, 57 and 85
- evaluation of intra-subject variability in PK between days 8, 57 and 85
- fluctuation on Day 85
- swing on Days 8, 57 and 85.

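### The SAP plans CL/F and Vz/F for metabolite M3 from the CPL409116 dose, and MRT for M3 with zero input time; none of these is M3's own clearance, volume or residence time

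*SAP*

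**What the plan says.** SAP 4.2.17 opens its parameter list with a sentence on scope: "PK parameters listed below will be estimated for both CPL409116 and its metabolite M3, if data permits". Two sub-lists follow, one of protocol parameters and one of exploratory parameters. The sentence precedes both.

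The exploratory sub-list contains three Day 85 parameters that matter here:

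- CL/F: "apparent systemic clearance, will be calculated as dose administered in dosing interval divided by" AUCtau at steady state. F is defined as the absolute availability of the product by the oral route.
- Vz/F: "apparent volume of distribution, calculated as" Dose/(Kel × AUCtau).
- MRT: "Mean Residence Time will be calculated for Day 85 as ratio of" AUMC(0–∞) to AUCtau, with the added condition that "MRT will be calculated under assumption that mean input time is 0".

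None of the three entries is limited to the parent.

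SAP 4.15 says the exploratory analysis "will be performed if data permits for both CPL409116 and M3 individually for each subject". Its list includes "evaluation of changes in CL/F" on Day 85 between doses, followed by the same item for Vz/F. MRT is not in the 4.15 list. A molar basis is stated there for the metabolite-to-parent ratios only.

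The dosed compound is CPL409116 at 60, 120 or 240 mg twice daily (SAP 2.2). The protocol's M3 endpoints are AUC(0–6h), Cmax, Tmax, T1/2 and Kel (synopsis, Criteria for Evaluation; repeated in SAP 2.1.2). The protocol does not ask for CL/F, Vz/F or MRT for M3.

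**The concern.** The numerator of CL/F and Vz/F is a dose. For M3 the only dose available is the parent's, and only part of that dose becomes M3. F, as the SAP defines it, has no term for that part. A programmer who follows the SAP as written will produce M3 columns labelled clearance and volume that mix M3's disposition with how much M3 is formed.

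The comparison between doses is where this could mislead. If the share of dose converted to M3 changes across the 60, 120 and 240 mg arms, M3 CL/F and Vz/F will change even when M3 elimination does not. The results go into the pharmacokinetic report attached to the Clinical Study Report (end of SAP 4.15).

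MRT has a different fault. Its formula contains no dose, but M3 enters plasma by formation from an orally absorbed parent, so a zero mean input time cannot describe it.

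**Working it through.** The documents state no M3 clearance, volume or residence time, so there is no planned figure to reproduce. The check applies the SAP formulas to M3, first in algebra and then in a numerical model.

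**Algebra (linear kinetics, steady state).** Let fm be the fraction of absorbed parent converted to M3, and r the molecular-weight ratio M3/parent. The M3 mass formed per dosing interval is F × fm × r × Dose, so

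- AUCtau,M3 = F × fm × r × Dose / CL_M3
- Dose/AUCtau,M3 = CL_M3 / (F × fm × r)
- Dose/(Kel × AUCtau,M3) = CL_M3 / (F × fm × r × Kel), where Kel is the observed M3 terminal slope
- AUMC(0–∞)/AUCtau for M3 = MRT_M3 + MRT_parent + mean absorption time

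The first ratio equals CL_M3/F only if fm × r = 1. The protocol gives the parent's molecular weight (section 6.1, 498.55 g/mol). The documents give neither M3's molecular weight nor fm.

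**Numerical check.** One compartment each for parent and M3, 12-hourly dosing to steady state, last dose followed to elimination. All inputs are assumed for illustration and none is from the documents: F = 0.5, absorption rate 1/h, parent CL 20 L/h and V 100 L, M3 CL 10 L/h and V 40 L, r = 1. The reference values are CL_M3/F = 10/0.5 = 20 L/h, V_M3/F = 40/0.5 = 80 L and MRT_M3 = 40/10 = 4 h.

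| fm | Dose/AUCtau for M3 (L/h) | ratio to CL_M3/F | Dose/(Kel × AUCtau) for M3 (L) | SAP MRT for M3 (h) |
|---|---|---|---|---|
| 0.05 | 400 | 20 | 2017 | 10.0 |
| 0.10 | 200 | 10 | 1008 | 10.0 |
| 0.25 | 80 | 4 | 403 | 10.0 |
| 0.50 | 40 | 2 | 202 | 10.0 |
| 1.00 | 20 | 1 | 101 | 10.0 |

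Four things follow.

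1. The clearance column equals 10/(0.5 × fm) exactly. The ratio to CL_M3/F is 1/fm, so an fm of 10–50% gives 10-fold down to 2-fold.
2. The volume column carries the same divisor and a second distortion. With these inputs the M3 terminal slope is governed by the parent (0.198/h, against a true M3 rate of 10/40 = 0.25/h). At fm = 0.10, V_M3/(F × fm) is 40/(0.5 × 0.10) = 800 L, but the formula returns 1008 L, and 1008/800 = 1.26 = 0.25/0.198.
3. MRT is 10 h at every fm: 4 h for M3, 100/20 = 5 h for the parent and 1 h for absorption. For the parent the same formula gives 5 + 1 = 6 h.
4. At fixed fm = 0.25, doses of 60, 120 and 240 mg all return 80 L/h, 403 L and 10 h for M3. A difference specific to M3 therefore appears when formation changes with dose. If fm fell from 0.30 to 0.20 between arms (assumed) with M3 elimination unchanged, M3 CL/F would rise by 0.30/0.20 = 1.5, that is by 50%.

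**The case against.** The best reply is that parent-only estimation was intended. F is defined as the availability of the product, which describes the dosed compound. The dose-proportionality analysis in SAP 4.15, which includes T1/2, CL/F and Vz/F, states its decision rule for CPL409116 parameters only. On this view the fault is a loose scope sentence. That may well be so, but the scope is stated for both analytes in 4.2.17 and again in 4.15. The proviso about the data permitting concerns availability of data and does not select an analyte. A sentence that contradicts the intent still needs correcting.

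A second reply is that the report contains its own safeguards: molar metabolite-to-parent ratios, parent/M3 ratios compared between doses with 90% confidence intervals, and M3 half-life. These would caution an attentive reader, but they cannot fully separate formation from elimination and do not correct the label.

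A third reply is that zero input time also fails for the oral parent. That stands. For the parent it adds absorption time; for M3 it adds the parent's whole residence time as well.

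Several stronger readings should not be drawn. A reader might infer that M3 MRT is derived from the parent dose or depends on the fraction converted; the SAP formula has no dose term, and the model gives the same MRT at every fraction. A reader might infer that the sponsor does not know the fraction converted; the earlier clinical results (protocol 2.3 and 2.4) are not in the available text, so one can say only that the documents do not give it. A reader might also infer that a secondary endpoint is compromised because the PK objective names M3; the protocol-listed M3 parameters do not include these three.

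**Conclusion.** The point holds as a minor one. Read as written, the SAP produces M3 CL/F and Vz/F that are M3 clearance and volume divided by F times the fraction converted, without a molar correction, and an M3 MRT that includes parent residence and absorption time. None of them describes M3's own disposition. The first two are also compared between dose arms, where a change in formation would read as a change in M3 clearance or volume.

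The size cannot be fixed from the documents. The 2- to 10-fold figure rests on an assumed conversion of 10–50% and ignores the molecular-weight ratio. It is measured against CL_M3/F, not against M3's true clearance, and is not a prediction for this compound. The algebra assumes linear kinetics.

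All three parameters are listed as exploratory, and SAP 4.15 describes that work as outside the protocol. No efficacy, safety or protocol-listed PK endpoint depends on them.

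**What to change.** In SAP 4.2.17, state that CL/F, Vz/F and MRT are calculated for CPL409116 only. In SAP 4.15, limit the CL/F and Vz/F comparisons in the same way; MRT needs no change there. Keep the M3 exposure parameters, the protocol-listed M3 endpoints and the molar metabolite-to-parent ratios as planned.

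If M3 values are still wanted, compute them on a molar basis, label them CL/(F × fm) and Vz/(F × fm), and drop MRT for M3.

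The cost is a sentence in each section and fewer outputs. Little is lost: Dose/AUCtau for M3 is only the reciprocal of its dose-normalised AUCtau. The restriction agrees with the protocol's M3 parameter list and with the parent-only decision rule already in 4.15.
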